2. STUDY PROCEDURES

a. Procedures

Unite Here Health will institute a novel program focused on providing patients with a lay health coach who will engage patients with goals of care after a diagnosis of cancer. Unite Here Health will enroll patients into the study after a new diagnosis of cancer or after a diagnosis of cancer that has progressed to a worsening stage. Unite Here Health staff will identify patients for the program through primary care physicians, oncologist referrals, and hospitalization daily notice of admissions and emergency department reports which Unite Here Health routinely receives as part of usual care. Patients without capacity to consent verbally will not be eligible for the study.

The Unite Here Health staff will contact eligible patients by telephone to introduce the study. If the patient is interested, he/she will be randomized into the usual oncology care arm versus the lay health worker intervention arm. Patients randomized into the intervention will be assigned a lay health worker who will contact the patient to begin the intervention. The intervention includes: education on early advance care planning,

documenting goals of care, assessing symptoms, and coordinating community services (such as home health, home visits, and home hospice).

The Unite Here Health staff, as part of their usual assessments, will conduct the following assessments for patients enrolled in the intervention and the usual oncology care arm at time of randomization and at 6 and 12 months after enrollment: a satisfaction with decision-making survey to compare changes in satisfaction, a patient activation measure survey (PAM survey), and the Functional Assessment of Cancer Therapy - General quality of life survey. At these time points, additional data collected as part of usual care will also be assessed for each patient. This includes: healthcare utilization (total number of emergency department visits and hospitalizations, referral to palliative care, and hospice receipt). This data will be abstracted from the patients' claims data that Unite Here Health routinely reviews and collects.

b. Procedure Risks

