The risks to subjects will be minimized as this is a study that provides usual oncology care. As part of the study intervention, additional support services will be provided to patients. Usual care procedures at the local site ensure sound procedures to minimize data sharing risk. There are no identifiers that will be collected or shared with the Stanford PI.

c. Use of Deception in the Study

No deception will be used.

d. Use of Audio and Video Recordings

No recordings will occur.

e. Alternative Procedures or Courses of Treatment

The study could improve documentation of patients' overall goals of care and could lead to a reduction in unwanted healthcare utilization. No standard of treatment will be withheld from patients. There are no potential risks to the patients involved in the study other than breach of confidentiality however no identifiers will be collected or shared with Stanford PI in the analysis of the data.

f. Will it be possible to continue the more (most) appropriate therapy for the participant(s) after the conclusion of the study?

Yes

g. Study Endpoint(s)

The primary endpoint is the Edmonton Symptom Assessment System (ESAS) at 12 months.

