5. RISKS

a. Potential Risks

As part of the study, patients will receive either usual care or will be assigned into the intervention. Patients assigned to the intervention will receive a lay health coach assigned to educate patients in goals of care, assist with symptom assessments, and coordinate community care (such as home hospice, home health services). All patients in the study will receive 3 surveys at baseline, 6 and 12 months after study enrollment: satisfaction with decision, patient activation, and quality of life assessment. receive satisfaction

surveys with their care (CAPHS-G). These will be anonymous surveys and will not be linked to the patient.

b. Procedures to Minimize Risk

We will not obtain identifiable records. For analysis purposes, all patients enrolled into the study will be assigned a unique identifier number. Data will be provided to the Stanford PI in aggregate. Patients will be coded and no direct identifiers will be linked to the patient. All data will be kept in a secure REDCAP database without any patient identifiers other than a unique identifier code.

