- ❖ Identify symptom control resources, which the oncologist may later prescribe as appropriate (including palliative care resources).

- Note: Here is a good place to address palliative care and begin the intake/ESAS. In addition, connect the patient with individual and group-based opportunities (support groups at the Cancer Institute) for emotional support involving interaction with trained professionals and other people undergoing similar health challenges
- ❖ Invite and encourage the patient to include anyone in the conversation such as family/caregiver and encourage the patient to include anyone who may potentially be attending future oncology appointments with the patient. Ask patient “are there any members of your family that you think will be part of your care?”
 - Note: If necessary, offer to reschedule the call to accommodate patient’s request.
- ❖ Provide ESAS for baseline assessment

Prior to each patient’s first oncologist appointment:

Educational Materials

- ❖ LHW will discuss educational materials such as videos/handouts with patients
- ❖ All cancer patients will be educated on the general topics of chemotherapy, radiation, and surgical approaches to treating cancer and potential side effects.
- LHW will discuss available handouts and reading materials with patients during the initial phone conversation
 - Front office staff will provide patients with handouts for their specific diagnosis, chemotherapy and symptom management (constipation, diarrhea, nausea, etc.) upon check out

Edmonton Symptom Assessment System (ESAS)

- 1) During the initial phone conversation the LHW will screen patients for symptom management using Edmonton Symptom Assessment System (ESAS) tool (attached)
- 2) After the initial consultation, LHW will review patient list with Physician Assistant to determine patient risk stratification and will contact and screen all high-risk patients via telephone on a weekly basis and all low risk patients on a monthly basis
- 3) LHW will input data into Rabbit EHR via ESAS/PHQ-9 template
- 4) Physician Assistant will review findings of ESAS results through EHR and if patient scores 4 or higher PA will notify the treating oncology practitioner and initiate usual care process for identified symptom management
- 5) Treating oncology practitioner must review/treat and agree with appropriate orders for any positive findings noted on the ESAS

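### The primary endpoint, ESAS at 12 months, has no described collection in the usual-care arm, and the only described collection is by the lay health workers who deliver the intervention

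*Protocol*

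**What the plan says.** Section 2g sets the endpoint: "The primary endpoint is the Edmonton Symptom Assessment System (ESAS) at 12 months".

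Section 2a sets what is measured in both arms. It begins "The Unite Here Health staff, as part of their usual assessments, will conduct the following assessments" and gives the times as "at time of randomization and at 6 and 12 months after enrollment". The instruments are a decision-making satisfaction survey, "a patient activation measure survey (PAM survey), and the Functional Assessment of Cancer Therapy - General quality of life survey". Utilization is added from claims data. Section 5a restates the schedule: "All patients in the study will receive 3 surveys at baseline, 6 and 12 months after study enrollment", and names satisfaction with decision, activation and quality of life.

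Section 2a also says who has a lay health worker: "Patients randomized into the intervention will be assigned a lay health worker who will contact the patient to begin the intervention". It lists among the components of the intervention "documenting goals of care, assessing symptoms, and coordinating community services".

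Apart from section 2g, ESAS appears only in Appendix 1, whose title is that of a CareMore and Oncology Institute quality improvement pilot. There, "During the initial phone conversation the LHW will screen patients for symptom management using Edmonton Symptom Assessment System (ESAS) tool", followed by weekly screening for high-risk and monthly screening for low-risk patients. A later heading of the same appendix has the research team do all surveys at enrollment and at 5 months.

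**The concern.** A primary endpoint must be measured in both arms, at the same time and in the same way. Here the endpoint sentence fixes a time, but no procedure or assessor is described for usual-care patients. In the intervention arm the score would be taken by the person delivering the intervention, during calls that are part of it.

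Two harms are possible, depending on what happens in practice. If staff follow the text, there are no control values and no primary comparison. If staff improvise for controls, collector and method differ by arm, and any systematic difference between them is read as a treatment effect. ESAS not collected at 12 months cannot be recovered later.

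Appendix 1 adds separate conflicts on who does the surveys, when, and in which patients. Those concern the secondary surveys and the population, not the claims outcomes.

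**Working it through.** **1. Where ESAS is and is not.**

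| Place in the protocol | Arm | Instruments | Times | Assessor |
|---|---|---|---|---|
| 2a, surveys | both | satisfaction, PAM, FACT-G | 0, 6, 12 months | Unite Here Health staff |
| 2a, further data | both | utilization from claims | same | abstracted |
| 5a | both | the same three domains | 0, 6, 12 months | not stated |
| 2g | not stated | ESAS | 12 months | not stated |
| Appendix 1, ESAS | lay health worker contacts | ESAS | first call, then weekly or monthly | lay health worker |
| Appendix 1, surveys | not stated | all surveys | 0, 5 months | research team |

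ESAS is 0 of the 3 instruments planned at the 3 both-arm time points. The claims item cannot fill the gap, because ESAS is a patient-reported score. Appendix 1 names no 12-month assessment.

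**2. Could Appendix 1 cover controls?** It speaks of all patients and does not name an arm. Read that way, controls would receive lay health worker calls, which contradicts section 2a and removes the contrast between arms. Read as intervention-only, controls have no ESAS. Neither reading gives a usable comparison.

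**3. Patients affected.** Planned enrollment is 180 (section 4a). The allocation ratio is not stated. Assuming 1:1, controls are 180/2 = 90; assuming 2:1, they are 180/3 = 60.

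**4. If controls are assessed differently (scenario, all inputs assumed except the 180).** Take an unadjusted two-sample comparison at two-sided 5%, no true effect, and a shift of d SD due to collection alone.

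- SE = √(1/n₁ + 1/n₂), z = d/SE
- False-positive rate = P(Z > 1.96 − z) + P(Z < −1.96 − z)

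For 90 v 90, SE = √(1/90 + 1/90) = 0.149, so d = 0.1, 0.2 and 0.3 give z = 0.67, 1.34 and 2.01.

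| Assessed | SE | d = 0.1 | d = 0.2 | d = 0.3 |
|---|---|---|---|---|
| 90 v 90 | 0.149 | 10.3% | 26.9% | 52.1% |
| 63 v 63 (30% lost) | 0.178 | 8.7% | 20.2% | 39.1% |
| 120 v 60 | 0.158 | 9.7% | 24.4% | 47.5% |

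**5. Survey schedule (secondary).** Planned forms, before deaths and dropout: 3 instruments × 3 rounds × 180 = 1,620. The 6- and 12-month rounds are 3 × 2 × 180 = 1,080, or 67%. If the appendix line overrode sections 2a and 5a, and if its surveys are these same three, those 1,080 would be replaced by one 5-month round of 3 × 180 = 540.

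**6. Population.** Appendix 1 takes new stage 3 or 4 cancer or hematologic malignancy. Sections 4a and 4f admit any new, relapsed or progressive cancer. Sections 1a and 6 speak of advanced cancer.

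**The case against.** The strongest objection is that the slip may lie in section 2g and not in section 2a. The purpose, background and benefits sections speak of satisfaction, quality of life and utilization, with activation in the purpose; none names symptom burden, and the instruments in section 2a match them. That stands as an observation, and naming a primary endpoint already collected in both arms would also remove the contradiction. It does not remove the defect, and keeping the declared endpoint is the more conservative repair.

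A second objection is that, if Appendix 1 belongs to another project, its 5-month line is that project's schedule and the problem is only a misplaced appendix. Its origin is an inference from the title; the appendix is part of this protocol, so the conflict is real. If it is set aside altogether, ESAS has no described collection in either arm.

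Third, weekly or monthly calls continued over the 12 months of enrollment would give intervention patients a score near month 12. That is fair, and it places the main gap in the control arm.

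Fourth, the error rates in step 4 rest on assumptions and describe a situation the protocol does not state. That is also fair. They illustrate what improvised collection could do; the finding does not depend on them. The form count likewise is a worst case. It also leaves out a further satisfaction survey mentioned in a garbled sentence of section 5a.

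Finally, a statistical analysis plan could not close the gap. Who administers the primary instrument to controls is a protocol procedure.

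**Conclusion.** The concern holds: the protocol is wrong as written and must be fixed. Its procedures describe no collection of the primary endpoint in the usual-care arm, which is 90 patients under assumed 1:1 allocation or 60 under 2:1. In the intervention arm the only described collection is by the person delivering the intervention. This conclusion rests on the text alone.

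The size of any bias from differing collection is unknown. Over an assumed shift of 0.1 to 0.3 SD, the false-positive rate would be about 10% to 52% with all 180 assessed 1:1, and about 9% to 39% with 30% lost. The survey-timing and population conflicts are real but lesser, and would not by themselves make this a must-fix point.

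**What to change.** - Add ESAS to the both-arm assessments in section 2a, at least at 12 months and preferably also at randomization before any lay health worker contact. Make section 5a agree.
- Have the same Unite Here Health staff collect it by the same method in both arms, separately from the lay health worker's program calls.
- Record it under the unique identifier of section 5b, and reconcile the statement in section 5a that surveys are anonymous and unlinked, so that baseline and 12-month scores can be paired.
- Delete the appendix survey line or align it with randomization, 6 and 12 months.
- Remove or adapt Appendix 1, state which arm it covers, and reconcile its population and workflow with sections 1a, 2a, 4 and 6. Which clinical workflow applies is for the investigators to decide.

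The cost is a protocol amendment and one short questionnaire at contacts already planned: 180 forms for 12 months only, or 2 × 180 = 360 with baseline, before deaths and dropout. No extra patients or contacts are needed.

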3. BACKGROUND

a. Past Experimental and/or Clinical Findings

We implemented a trial at the VA Palo Alto Health Care System that assigned a lay health worker to patients with advanced cancer. In this study, we found improvements in patient satisfaction and reduction in healthcare utilization at the end of life. However, it is unclear if such an effort will improve quality of life and improve satisfaction and reduce healthcare utilization outside of the VA system.

b. Findings from Past Animal Experiments

None

4. PARTICIPANT POPULATION

a. Planned Enrollment

At the local site, Unite Here Health will enroll a total of 180 patients into the study. Inclusion criteria are as follows:

1. Newly diagnosed patients with a cancer diagnosis.
2. Patients with any relapse or progressive disease (any cancer diagnosis) as identified by imaging or biopsy and confirmed by physician.
3. The patients must be 18 years or older.
4. Patients must have the capacity to verbally consent.

The total number of patients with cancer who are members of Unite Here Health are 200 per year. Therefore we anticipate that we will feasibly be able to enroll 180 patients into the study during the first 18 months.

b. Age, Gender, and Ethnic Background

The age range is > 18, gender is both male and female, and ethnic population is Hispanic, Asian/Pacific Islander, Non-Hispanic White, Non-Hispanic Black, American Indian, and Alaskan Native.

c. Vulnerable Populations

We will not enroll children or pregnant women. The study will be offered to all patients regardless of economic status. Patients who are unable to consent to participation will not be included.

d. Rationale for Exclusion of Certain Populations

Children are not included because the study is focused on adult patients with cancer. Additionally, Unite Here Health does not have any members less than the age of 18.

e. Recruitment Details

All eligible patients at Unite Here Health will be identified and referred into the study by the primary oncologist, primary care physician, or through daily inpatient and emergency

department reports which are routinely sent to the Unite Here Health staff as part of usual care.

f. Eligibility Criteria

i. Inclusion Criteria

1. Newly diagnosed patients with a cancer diagnosis.
2. Patients with any relapse or progressive disease (any cancer diagnosis) as identified by imaging or biopsy and confirmed by physician.
3. The patients must be 18 years or older.
4. Patients must have the capacity to verbally consent.

ii. Exclusion Criteria

Inability to consent to the study due to lack of capacity as documented by the referring physician.

Patients without a newly diagnosed malignancy or patients without relapse of disease.

g. Screening Procedures

There are no screening procedures for enrollment in the study.

h. Participation in Multiple Protocols

There are no other studies ongoing at Unite Here Health that may lead to dual enrollment in studies.

i. Payments to Participants

No payment will be provided.

j. Costs to Participants

No costs will be charged to the participant.

k. Planned Duration of the Study

Patients will be enrolled in the study for a total of 12 months from the date of enrollment. Analysis of participant data in aggregate is estimated to take 8 months.

5. RISKS

a. Potential Risks

As part of the study, patients will receive either usual care or will be assigned into the intervention. Patients assigned to the intervention will receive a lay health coach assigned to educate patients in goals of care, assist with symptom assessments, and coordinate community care (such as home hospice, home health services). All patients in the study will receive 3 surveys at baseline, 6 and 12 months after study enrollment: satisfaction with decision, patient activation, and quality of life assessment. receive satisfaction

surveys with their care (CAPHS-G). These will be anonymous surveys and will not be linked to the patient.

b. Procedures to Minimize Risk

We will not obtain identifiable records. For analysis purposes, all patients enrolled into the study will be assigned a unique identifier number. Data will be provided to the Stanford PI in aggregate. Patients will be coded and no direct identifiers will be linked to the patient. All data will be kept in a secure REDCAP database without any patient identifiers other than a unique identifier code.

6. BENEFITS

The benefit from this study will help to inform whether a lay health coach can improve patient satisfaction, quality of life, and reduce healthcare utilization for patients diagnosed with advanced cancer.

7. PRIVACY AND CONFIDENTIALITY

All participant information and specimens are handled in compliance with the Health Insurance Portability and Accountability Act (HIPAA) and privacy policies of Stanford University, Stanford Health Care, and Stanford Children's Health.

Appendix 1: Patient Procedures

Stanford –CareMore-Oncology Institute of Hope and Innovation- Lay Health Worker Symptom Assessment Quality Improvement Pilot

Identifying Patients

- ❖ All patients with newly diagnosed cancer Stage 3 or 4 or hematologic malignancies requiring Medical Oncology will be included in the program.
- 1) Patients will be categorized as either "High Risk" or "Low-Risk" based on the following criteria:
- 1) High Risk: All metastatic cancer patients as well as all patients on active chemotherapy, all patients with symptom scores 4 or above, or any change in symptom of greater than 2 points from prior assessment
- 2) Low Risk: Patients who are not on chemotherapy and are undergoing routine follow-up/surveillance, who have no symptom scores of 4 or above, and no change in symptom scores
- 3) Three months after a non-metastatic patient has completed adjuvant chemotherapy or treatment, he/she will be transitioned to low-risk status unless trigger event occurs as above.

Patient Engagement

- LHW will contact all patients via telephone who meet the criteria prior to their first oncology appointment
- LHW will schedule an initial oncology consultation appointment with the patient within 5 days of initial contact
- LHW will discuss program
- LHW will prepare the patient for their upcoming initial consultation with an oncologist
- LHW will invite and encourage the patient to include anyone in the conversation such as family/caregiver and encourage the patient to include anyone who may potentially be attending future oncology appointments with the patient.
 - If necessary, the LHW will offer to reschedule the call to accommodate patient's request for others to be present during conversation.
- LHW will provide contact information for patients to use in the event of any future triggers and provide a list of all the appropriate triggers to the patient and the care circle.
 - Triggers Include:
 - Disease progression
 - Unexpected side effects
 - Potential change of treatment
 - ED visit or hospital use
 - If for any reason patient does not feel comfortable
 - Life situation changes in a manner that potentially impacts symptoms
 - Oncologist refers patient back to the LHW
 - Patient family members need education/clarification/support

Introduction of HVCCP

- ❖ Explain the purpose is to help patients maintain symptom relief.
 - The LHW is here to support the patient throughout this process
- ❖ Identify symptom control resources, which the oncologist may later prescribe as appropriate (including palliative care resources).

- Note: Here is a good place to address palliative care and begin the intake/ESAS. In addition, connect the patient with individual and group-based opportunities (support groups at the Cancer Institute) for emotional support involving interaction with trained professionals and other people undergoing similar health challenges
- ❖ Invite and encourage the patient to include anyone in the conversation such as family/caregiver and encourage the patient to include anyone who may potentially be attending future oncology appointments with the patient. Ask patient “are there any members of your family that you think will be part of your care?”
 - Note: If necessary, offer to reschedule the call to accommodate patient’s request.
- ❖ Provide ESAS for baseline assessment

Prior to each patient’s first oncologist appointment:

Educational Materials

- ❖ LHW will discuss educational materials such as videos/handouts with patients
- ❖ All cancer patients will be educated on the general topics of chemotherapy, radiation, and surgical approaches to treating cancer and potential side effects.
- LHW will discuss available handouts and reading materials with patients during the initial phone conversation
 - Front office staff will provide patients with handouts for their specific diagnosis, chemotherapy and symptom management (constipation, diarrhea, nausea, etc.) upon check out

Edmonton Symptom Assessment System (ESAS)

- 1) During the initial phone conversation the LHW will screen patients for symptom management using Edmonton Symptom Assessment System (ESAS) tool (attached)
- 2) After the initial consultation, LHW will review patient list with Physician Assistant to determine patient risk stratification and will contact and screen all high-risk patients via telephone on a weekly basis and all low risk patients on a monthly basis
- 3) LHW will input data into Rabbit EHR via ESAS/PHQ-9 template
- 4) Physician Assistant will review findings of ESAS results through EHR and if patient scores 4 or higher PA will notify the treating oncology practitioner and initiate usual care process for identified symptom management
- 5) Treating oncology practitioner must review/treat and agree with appropriate orders for any positive findings noted on the ESAS
- 6) PA will place necessary orders for referrals and notify the treating oncology practitioner via Rabbit e-mail

- ❖ Referrals will be requested via the CareMore Utilization Management Provider Portal

Patient Symptom Complaints/Triages

- When LHW pilot patients contact staff with a symptom related complaint, staff will create and assign a triage message to the appropriate provider per the most up to date Mid-Level Triage schedule

- The oncology PA will then assess and treat the patient's symptoms per the symptom management algorithms provided to them
- PA will follow each triage message to ensure that the treating oncology practitioner is following all LHW protocols

After Hour Calls

- When a patient contacts exchange after hours (between 5pm-8:30am Monday-Friday and all day Saturday/Sunday), the on-call treating oncology provider will be paged per the standing protocol.
- All patients will be instructed to identify themselves as pilot program patients to both the exchange service as well as to the treating oncology provider who takes the call.
- The treating oncology provider will assess and treat the patient's symptoms per the symptom management algorithms
- If the treating oncology provider feels that patient requires urgent evaluation which cannot wait until business hours, patient will be referred to the nearest emergency department.
- The treating oncology provider is required to notify the PA about the call on the next business day. The message to the PA will include the reason for call, recommended treatment and outcome.
- PA will ensure that the treating oncology provider has followed symptom management algorithms
- PA will recommend more aggressive symptom management to the treating oncology practitioner if applicable.

Patient Satisfaction, Mental and Emotional Health

- All Surveys are to be done by research team and will be conducted when patients enroll and again 5-months post enrollment

No Shows

- If a patient is a no show to his/her office visit appointment LHW will contact the patient 3 times (1 time per week) in an effort to reschedule patient's appointment
- In the event the LHW is unable to reach patient/reschedule patient's appointment, LHW will send an Outlook e-mail to PA/[name]/[name]/Caremore

Exit Criteria

- ❖ Patient Preference
 - If patient notifies staff of the Oncology Institute he/she does not wish to continue care, staff must place a triage the reason patient does not want to continue care at the practice and must notify LHW/PA/[name]/[name] and the treating oncology practitioner via Rabbit e-mail
 - Death
 - Staff must follow standard office policy for documenting and marking the chart whenever a patient expires
 - ❖ Staff must notify the LHW and site leader as well as the treating oncology practitioner
 - ❖ LHW will ensure that chart has been appropriately documented in EHR
- ❖ Disqualification
 - ❖ If at any point during the staging/screening process a patient is noted to not have invasive cancer, he/she will be removed from the study list
- ❖ Date and reason of exit will be documented in EHR

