1. PURPOSE OF THE STUDY

a. Brief Summary

The purpose of the LEAPS program is to understand how a trained lay health worker who engages with newly diagnosed patients after a diagnosis of an advanced stage of cancer can help to improve patient satisfaction with their decision-making, activation, quality of life, and healthcare resource utilization.

b. Objectives

We hope to better understand how to help improve patients' care after a diagnosis of advanced cancer. We want to better understand the influence of a local lay health coach on improving patient's efficacy, quality of life, and satisfaction. We also want to know the impact of the program on healthcare resource utilization (emergency department, hospitalization, hospice utilization).

c. Rationale for Research in Humans

Because this is a novel program focused on helping patients better understand their goals of care, human subjects must be used for this project.

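### Appendix 1 is written for another organisation's symptom pilot, and its survey schedule and entry rule conflict with the protocol body

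*Protocol*

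**What the plan says.** **Setting.** The body describes a randomized study run by Unite Here Health. Appendix 1 is headed "Lay Health Worker Symptom Assessment Quality Improvement Pilot", naming Stanford, CareMore and the Oncology Institute. It works through the CareMore referral portal and Oncology Institute staff, and it mentions neither Unite Here Health nor a usual-care arm.

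**Surveys.** Section 2a has Unite Here Health staff carry out three instruments (decision satisfaction, patient activation, quality of life) in both arms at randomization, 6 months and 12 months. Section 5a repeats the three time points. Appendix 1, under its heading on satisfaction and mental and emotional health, has the research team do all surveys at enrolment and at 5 months.

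**Entry.** Section 4 lists "Newly diagnosed patients with a cancer diagnosis" and "Patients with any relapse or progressive disease (any cancer diagnosis) as identified by imaging or biopsy and confirmed by physician". Appendix 1 states: "All patients with newly diagnosed cancer Stage 3 or 4 or hematologic malignancies requiring Medical Oncology will be included in the program".

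**Allocation.** In Section 2a an interested patient is phoned by Unite Here Health staff, and then "he/she will be randomized into the usual oncology care arm versus the lay health worker intervention arm". Only those allocated to the intervention are given a worker. Appendix 1 says "LHW will contact all patients via telephone who meet the criteria prior to their first oncology appointment" and does not mention allocation.

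**Primary endpoint.** Section 2g names ESAS at 12 months.

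**The concern.** Section 2a gives the intervention content in one sentence, and Section 5a partly repeats it. Appendix 1 is therefore the only step-by-step account of the worker's job in the document, and site staff would naturally work from it. Nothing says that the body prevails where the two differ, or how to adapt the appendix to Unite Here Health.

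The stakes are practical. A team that followed the appendix schedule would collect a 5-month survey that the body does not ask for, and nothing at 6 or 12 months. A team that followed the appendix entry rule would screen for a narrower population than Section 4 defines. The primary endpoint is also exposed, because the only text on how ESAS is obtained sits in this appendix.

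**Working it through.** No statistical formula applies. The check sets the two texts side by side.

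| Item | Body | Appendix 1 | Result |
|---|---|---|---|
| Survey times (months) | 0, 6, 12 (2a, 5a) | 0, 5 | Conflict |
| Who surveys | Unite Here Health staff (2a) | Research team | Conflict |
| Entry, new diagnosis | Any cancer (Section 4) | Stage 3 or 4, or hematologic | Conflict |
| Entry, relapse or progression | Eligible (Section 4) | Not named as an entry route | Conflict |
| Arm | Worker for the intervention arm only (2a) | Not stated | Gap |
| First oncology visit | No rule | Call comes first; worker books the visit within 5 days | Gap for some patients |
| Advance care planning, goals of care | Listed (2a) | No step | Gap |

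**Surveys.** {0, 6, 12} and {0, 5} share only 0. So 1 of the 3 body time points agrees, and 0 of the 2 follow-up points.

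**Entry.** Of the two disease routes in Section 4, the appendix covers new diagnosis in part (earlier-stage solid tumours fall outside) and does not name relapse or progression. Disease progression appears in the appendix only as a trigger for patients already in the program. The documents do not give the share of the 180 patients affected, so the conflict is one of rules and not of a count.

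**Gaps.**
- Arm: the appendix is silent, and 2a supplies the answer.
- First visit: the steps suit a newly diagnosed patient found through primary care, an admission or an emergency department report. They do not suit a patient with relapse or progression, or one already seen by an oncologist.
- Content: 2a lists four components. Symptom assessment is covered in detail. Service coordination is partly covered through palliative care resources, support groups and referrals. The other two, advance care planning education and goals-of-care documentation, have no step.

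**ESAS.** The 2a assessment list has three instruments, and ESAS is not one of them. In Appendix 1 the worker gives ESAS on the first call, then weekly for high-risk and monthly for low-risk patients, and a score of 4 or more leads to symptom management. That is clinical screening by the person delivering the intervention. If the appendix is confined to the intervention arm, as 2a implies, the document describes no ESAS collection in usual care. On any reading it schedules no 12-month ESAS assessment.

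**The case against.** **The body is clear and no body section cites Appendix 1.** This is true, and 2a and 5a do state the 6- and 12-month surveys. But the appendix is part of the same protocol, and its schedule and entry rule are stated, not merely left open.

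**The appendix surveys might be a different set.** Their heading mentions mental and emotional health. But the rule covers all surveys and the heading also names satisfaction, so it overlaps with 2a.

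**The entry rule does not say that others are excluded, and part of the mismatch lies inside the body.** Both points stand. Section 1 speaks of a worker who "engages with newly diagnosed patients after a diagnosis of an advanced stage of cancer", and Section 6 hopes to "reduce healthcare utilization for patients diagnosed with advanced cancer". The stage limit fits those aims better than Section 4 does. The two entry rules still differ.

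**Stronger readings that a reader might infer.**
- That usual-care patients will get a worker, so that the ESAS contrast is diluted. Section 2a rules this out, and the appendix is silent rather than contrary. The protocol states no power, effect size or contact rate in controls, so no loss can be calculated from it.
- That advance care planning and goals-of-care work will not be delivered. The appendix omits these steps but does not cancel 2a, and coaching content may sit in material not shown.
- That the appendix contradicts the body throughout. Only surveys and entry are direct conflicts.

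A statistical analysis plan would not cure this: visit schedules, entry rules and intervention steps are protocol matters.

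**Conclusion.** The point holds for two direct conflicts. On surveys, the schedules share one of three time points and name different assessors. On entry, one of the two disease routes in Section 4 is not named and the other is covered only in part. The silence on arm, the first-visit steps and the two missing content steps are gaps that need a line of text; they are not contradictions.

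The consequence that matters most is for the primary endpoint: the only ESAS procedure described is worker-delivered, and none is described for usual care.

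That the appendix was carried over from another project is an inference from its heading and workflow. It is a strong one, but the documents do not say whether CareMore or the Oncology Institute has a role here. The loss of 6- and 12-month surveys would follow only if the appendix were used in place of the body. This should be corrected before the appendix is used to run the trial.

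**What to change.** Amend the Protocol as follows.

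1. In Appendix 1, replace the 5-month survey rule with baseline, 6 and 12 months, done by the staff named in 2a.
2. Replace the appendix entry rule with a reference to the Section 4 criteria. If the sponsor intends advanced disease only, Section 4 is the place to say so, and the reference will carry the change.
3. State that the worker procedures apply only to patients randomized to the intervention, and that the first-visit steps apply only where no oncology visit has yet taken place.
4. Add ESAS outcome collection to 2a for both arms at the baseline, 6- and 12-month contacts, separate from the worker's ESAS screening. Without this, step 3 would leave the primary endpoint described in one arm only.

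The same amendment can add the advance care planning and goals-of-care steps, or name the material that holds them.

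The cost is one protocol amendment and one short added instrument at contacts already planned for both arms.
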